5.2.20 Concomitant medication

A concomitant medication corresponds to any medication reported in the “PREVIOUS AND CONCOMITANT MEDICATIONS” form of the eCRF with a {medication start date \leq first treatment intake date and medication end date \geq first treatment intake date or ongoing} or with a {first treatment intake date \leq medication start date} (after application of missing dates replacement rules, see section 7.4).

STATISTICAL ANALYSIS PLAN		
InFlectis BioScience	Sponsor:	InFlectis BioScience
	Protocol Number:	P288ALS
VERSION 1.0 NOV 12, 2024		

5.2.21 Efficacy endpoints

- ALSFRS-R subscore:

Three subscores will be considered as follows:

- Bulbar subscore: sum of items 1-3
- Motor subcore: sum of items 4-9
- Respiratory subcore: sum of items 10-12

Subscore will be considered as missing if an item is missing.

Note: for motor subscore, item 5 will be considered at missing if item 5a and 5b are missing.

- Worsening (i.e. progression to a higher stage compared to baseline defined by ALS-MITOS score):

Non progression at 6 months (V4) and 3 (V3) months will be derived as follows:

- 0 if ALS-MITOS score is higher at 6 months (or 3 months) compared to ALS-MITOS score at baseline
- 1 if ALS-MITOS score is lower or equal at 6 months (or 3 months) compared to ALS-MITOS score at baseline
- Change in King's College score

Non progression at 6 months and 3 months will be derived as follows:

- 0 if King's College score is higher at 6 months (or 3 months) compared to baseline
- 1 if King's College score is lower or equal at 6 months (or 3 months) compared to baseline
- SVC: percentage of the predicted value for age and sex (%)

Percentage of the predicted value will be calculated according to the formula of predicted FVC in 'Multi-ethnic reference values for spirometry for the 3–95-yr age range: the global lung function 2012 equations' article of Quanjer.

STATISTICAL ANALYSIS PLAN		
InFlectis BioScience	Sponsor: Protocol Number:	InFlectis BioScience P288ALS
VERSION 1.0 NOV 12, 2024		

$$\% \text{ of the predicted value} = (\text{SVC} / M_{\text{predicted}}) * 100$$

Where

For man:

$$M_{\text{predicted}} = \exp(-11.2281 + 2.4135 * \ln(\text{Height in cm}) + 0.0865 * \ln(\text{Age}) + Mspline)$$

$$Mspline = 0.3298 - 1.1230 * (\text{Age}/100) + 2.8110 * (\text{Age}/100)^2 - 5.4811 * (\text{Age}/100)^3 + 3.5964 * (\text{Age}/100)^4 - 0.5884 * (\text{Age}/100)^5$$

For woman:

$$M = \exp(-10.4030 + 2.2633 * \ln(\text{Height in cm}) + 0.0234 * \ln(\text{Age}) + Mspline)$$

$$Mspline = 0.0745 + 0.6006 * (\text{Age}/100) - 1.0684 * (\text{Age}/100)^2 - 1.1308 * (\text{Age}/100)^3 + 0.9730 * (\text{Age}/100)^4 + 0.0643 * (\text{Age}/100)^5$$

For example, 40 years white man, height 185 cm, SVC of 5L:

$$\% \text{predicted value} = (5/5.79) * 100 = 86 \%$$

For example, 35 years white woman, height 170 cm, SVC of 2.5L:

$$\% \text{predicted value} = (2.5/4.16) * 100 = 60 \%$$

5.2.22 Laboratories data

- Triglycerides will be categorized as:
 - $\leq 1.71 \text{ mmol/L} (\leq 150 \text{ mg/dL}, \leq 1.5 \text{ g/L}, \leq 171 \text{ umol/L})$,
 - $[1.71; 3.42] \text{ mmol/L} ([150; 300] \text{ mg/dL}, [1.5; 3] \text{ g/L}, [171; 342] \text{ umol/L})$,
 - $[3.42; 5.7] \text{ mmol/L} ([300; 500] \text{ mg/dL}, [3; 5] \text{ g/L}, [342; 570] \text{ umol/L})$,
 - $[5.7; 11.4] \text{ mmol/L} ([500; 1000] \text{ mg/dL}, [5; 10] \text{ g/L}, [570; 1140] \text{ umol/L})$,
 - $> 11.4 \text{ mmol/L} (> 1000 \text{ g/L}, > 10 \text{ g/L}, > 1140 \text{ umol/L})$
- Glomerular Filtration Rate will be categorized as:
 - $< 15 ; [15; 29] ; [29; 44] ; [44; 59] ; [59; 90[; \geq 90 \text{ mL/min/1.73 m}^2$

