5.12.3.3 Analysis

Clinically significant abnormalities in laboratory values across the whole study will be summarized and listed.

For urinalysis parameters:

Shift tables in relation with normal, abnormal CS and abnormal NCS value from baseline to V3 and V4 will be presented for each parameter.

Urinalysis data will also be listed separately for each parameter.

For 24h protein test parameters:

Shift tables in relation with normal, abnormal CS and abnormal NCS value from baseline to V3 and V4 will be presented for the investigator's overall assessment.

STATISTICAL ANALYSIS PLAN			
InFlectis BioScience	Sponsor:	InFlectis BioScience	
	Protocol Number:	P288ALS	
VERSION 1.0 NOV 12, 2024			

A listing will also be presented for patients with at least one abnormal clinically significant of 24h protein test during the study.

For hematology, biochemistry, renal function, liver function and electrolytes parameters:

Each measurement (continuous data) will be categorized as below, within, or above normal range, based on ranges supplied by the laboratory used. Shift tables in relation to the normal range from Baseline to V3 and V4 will be presented for each parameter.

Laboratory data will also be listed separately for each parameter (indicating abnormal values at each applicable follow-up time point). Quantitative value at each visit with the change from baseline and relative change from baseline will be also presented in the listing.

Table 4: Specific rules for ULN and LLN by parameters

Parameter	Units	Below normal range	In normal range	Above normal range
Glomerular Filtration Rate	ml/min/1,73 m ²	<90	≥90	NA
Basophils	10 ³ /mm ³ ou 10 ³ /uL ou 10 ⁹ /L ou G/L	NA	<0.1	≥0.1
	%	Not analysable (will be converted by data management)		
Eosinophils	10 ³ /mm ³ ou 10 ³ /uL ou 10 ⁹ /L ou G/L	NA	<0.4	≥0.4
	%	Not analysable (will be converted by data management)		
Erythrocytes	10 ¹² /L, 10 ⁶ /mm ³ , 10 ⁶ /uL, T/L	<3.8	[3.8 ;5.5]	>5.5
Hemoglobin	g/dL	<12	[12 ;16]	>16
	g/L	<120	[120 ;160]	>160
Lymphocytes	10 ³ /mm ³ ou 10 ³ /uL ou 10 ⁹ /L ou G/L	<1,5	[1,500 ; 4]	>4
	%	Not analysable (will be converted by data management)		
Monocytes	10 ³ /mm ³ ou 10 ³ /uL ou 10 ⁹ /L ou G/L	<0.5	[0.5 ; 0.8]	>0.8
	%	Not analysable (will be converted by data management)		
Neutrophils	10 ³ /mm ³ ou 10 ³ /uL ou 10 ⁹ /L ou G/L	<1.5	[1.5 ; 7]	>7
	cells/mm ³	<1500	1500 et 7000	>7000

STATISTICAL ANALYSIS PLAN				
InFlectis BioScience	Sponsor:		InFlectis BioScience	
	Protocol Number:		P288ALS	

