VERSION 1.0 NOV 12, 2024				

	%	Not analysable (will be converted by data management)		
White blood cells, total	1000/uL, 10 ³ /mm ³ , 10 ³ /uL, 10 ⁹ /L et G/L	<4.5	[4.5 ; 11]	>11
Glucose	mg/dl	<70	[70 ; 110]	>110
	mmol/L	<4	[4 ; 6.1]	>6.1
	umol/L	<400	[400 ; 610]	>610
HDL cholesterol	g/L	<0.4	≥ 0,4	NA
	mg/dl	<40	≥ 40	NA
	mmol/L	<1.04	≥ 1.04	NA
LDL cholesterol	mg/dL	NA	<160	≥160
	mmol/L	NA	<4.1	≥4.1
Total Cholesterol	mg/dL	NA	<200	≥200
	mmmol/L	NA	<5	≥5
Triglycerides	g/L	NA	≤1.5	>1.5
	mg/dL	NA	≤150	>150
	mmol/L	NA	<1.71	>1.71
	umol/L	NA	<=171	>171
Alanine Aminotransferase	All units	NA	<ULN	>ULN
Aspartate Aminotransferase	All units	NA	≤ULN	>ULN
D-Dimers	All units	NA	≤ULN	>ULN
Direct Bilirubin	All units	NA	≤ULN	>ULN
Gamma Glutamyl Transferase	All units	NA	≤ULN	>ULN
Other parameters	All units	<LLN	[LLN ; ULN]	>ULN

If LLN is missing then all values below the ULN will be considered as in reference range.

If ULN is missing then all values above the LLN will be considered as in reference range.

If a value is <xx then:

- If the LLN = 0 or missing or NA then consider the value as in reference range
- Else consider the value as low reference range

If a value is >xx then:

- If the ULN is missing or NA then consider the value as in reference range
- Else consider the value as upper reference range

For Glomerular Filtration Rate:

If a value is >xx with xx<90 then consider value as below reference range

If a value is >xx with xx≥90 then consider value as in reference range

If a value is <xx then consider value as below reference range

STATISTICAL ANALYSIS PLAN		
InFlectis BioScience	Sponsor:	InFlectis BioScience
	Protocol Number:	P288ALS
VERSION 1.0 NOV 12, 2024		

Note: for all listing value of premature discontinuation and V3bis visit will be also presented when applicable.

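### The umol/L limits for triglycerides (SAP 5.2.22 and Table 4) and glucose (Table 4) are one tenth of the mmol/L limits printed beside them, so either the numbers or the unit label must be corrected

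*SAP*

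**What the plan says.** SAP 5.2.22 defines the triglyceride classes by limits at 1.71, 3.42, 5.7 and 11.4 mmol/L, with stated equivalents in mg/dL, g/L and umol/L. The fourth class is printed as "5.7; 11.4] \text{ mmol/L} ([500; 1000] \text{ mg/dL}, [5; 10] \text{ g/L}, [570; 1140] \text{ umol/L". The equivalents of the top class are printed as "> 1000 \text{ g/L}, > 10 \text{ g/L}, > 1140 \text{ umol/L". SAP 5.12.1.2 uses these classes to describe triglycerides.

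Table 4 in SAP 5.12.3.3 sets normal ranges. For triglycerides it puts 1.71 mmol/L beside 171 umol/L. For glucose it gives 4 to 6.1 mmol/L and, in another row, 400 to 610 umol/L.

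The text before the table says "Each measurement (continuous data) will be categorized as below, within, or above normal range, based on ranges supplied by the laboratory used". The table is then titled "Specific rules for ULN and LLN by parameters". It gives its own limits for triglycerides and glucose, and leaves the laboratory's own limits to a few named analytes and to a last row called "Other parameters". The classification feeds this output: "Shift tables in relation to the normal range from Baseline to V3 and V4 will be presented for each parameter".

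**The concern.** The limits in one row or class are meant to be the same limit in different units. A result should therefore get the same class whatever unit the laboratory used. With a tenfold gap, a result held in umol/L would be judged against a limit ten times too low.

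Two descriptive safety outputs would be affected: the triglyceride class description and the shift tables from baseline to V3 and V4. A patient with a normal baseline would already be counted as high, so a real rise from normal to high would appear as no change. The direction of an abnormality could also be lost, because a low glucose would read high. Safety is the trial's primary objective and hypertriglyceridaemia is a named AESI, so these tables will be read with some care.

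The SAP does not provide for such results to be converted first. Table 4 mentions conversion by data management only for white-cell differentials reported in per cent.

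**Working it through.** **Inputs.** Triglyceride limits from SAP 5.2.22 (the first repeated in Table 4) and glucose limits from Table 4.

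**Do the other units agree?** For triglycerides, mg/dL divided by mmol/L is 150/1.71 = 300/3.42 = 500/5.7 = 1000/11.4 = 87.72, one constant factor. In the first four classes mg/dL is exactly 100 times g/L. The AESI definition in SAP 5.2.19 also pairs 5.7 mmol/L with 5.0 g/L. For glucose the factor is 70/4 = 17.5 and 110/6.1 = 18.03, which is rounded but of the same order. Apart from the g/L entry in the top triglyceride class, only the umol/L entries are out of line.

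**The umol/L limits.** Expected umol/L = mmol/L × 1000. If the printed number is read as umol/dL, it equals mmol/L × 100.

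| Analyte | mmol/L | Expected umol/L | Printed umol/L | Printed/expected | Printed number read as umol/dL, in mmol/L |
|---|---|---|---|---|---|
| Triglycerides | 1.71 | 1710 | 171 | 0.1 | 1.71 |
| Triglycerides | 3.42 | 3420 | 342 | 0.1 | 3.42 |
| Triglycerides | 5.7 | 5700 | 570 | 0.1 | 5.7 |
| Triglycerides | 11.4 | 11400 | 1140 | 0.1 | 11.4 |
| Glucose | 4 | 4000 | 400 | 0.1 | 4.0 |
| Glucose | 6.1 | 6100 | 610 | 0.1 | 6.1 |

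The ratio is exactly one tenth at all six limits, in two sections and for two analytes. That rules out rounding or a stray digit. The umol/dL reading also fits at all six.

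**Effect on a triglyceride result truly held in umol/L** (classes of 5.2.22 numbered 1 to 5):

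| True value, mmol/L | Held as, umol/L | Intended class | Class from printed limits |
|---|---|---|---|
| 1.0 | 1000 | 1 | 4 |
| 1.2 | 1200 | 1 | 5 |
| 2.0 | 2000 | 2 | 5 |
| 6.5 | 6500 | 4 | 5 |
| 12 | 12000 | 5 | 5 |

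True values above 0.57 and up to 1.14 mmol/L (570 to 1140 umol/L) land in class 4, and normal values above 1.14 mmol/L land in class 5. In the shift table, a rise from 1.0 to 6.5 mmol/L should read normal to high. Against the printed limit of 171 both 1000 and 6500 are high, so it reads high to high.

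**Effect on glucose truly held in umol/L.** The normal range is 4000 to 6100 umol/L, all above 610, so every normal value reads high. A value of 3.5 mmol/L is 3500 umol/L; it should read low (3.5 < 4) but also reads high (3500 > 610). Truly high values of either analyte are still flagged high in Table 4.

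**Top triglyceride class.** It prints 1000 g/L beside 10 g/L, which cannot both hold. The lower classes list mg/dL in that position, and 10 g/L is 1000 mg/dL, so mg/dL is meant.

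**The case against.** The arithmetic is not in doubt; the objections concern weight.

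- **Harm needs two facts that the documents do not give.** Some results must be held in this unit, and the unit must truly be umol/L. This stands. Protocol Table 3 appears to send blood safety tests to local laboratories, and Table 4 has umol/L rows for these two analytes but not for the cholesterol measures. Both make a check reasonable, but neither shows that such results exist.
- **The outputs are descriptive and backed up.** This also stands. For laboratory values the SAP says "Quantitative value at each visit with the change from baseline and relative change from baseline will be also presented in the listing", and separately "Clinically significant abnormalities in laboratory values across the whole study will be summarized and listed". An error of this size would also be conspicuous in the tables.
- **The general sentence on laboratory-supplied ranges might override Table 4.** No sentence settles this. The table's title and its last row make it the natural reading that Table 4 governs these two analytes, but that is an inference. It does not touch the classes in 5.2.22, which do not depend on laboratory ranges.

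A reader might infer that the primary safety endpoints, or the hypertriglyceridaemia AESI, are compromised. The documents do not support that. The primary endpoints in Protocol section 2 are adverse events, not laboratory classes. The AESI cut-off is defined in mmol/L and g/L and its listing is set in mmol/L, and those figures agree with each other. Nor do the documents show that the numbers rather than the label are at fault.

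**Conclusion.** The plan is wrong as written: six distinct umol/L limits are one tenth of their mmol/L partners. Whether this changes any result is unknown. The possible effect runs from none (no results in that unit, or a unit that is really umol/dL) to misclassing nearly all triglyceride results, and all normal and low glucose results, that are truly held in umol/L. The share of such results is not stated and may be zero.

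The conclusion on the limits rests only on 1 mmol = 1000 umol. The conclusion on the shift tables also assumes that Table 4 governs triglycerides and glucose. Because the outputs are descriptive and the quantitative values are listed, this is a correction to make before programming, not a threat to the trial's conclusions.

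**What to change.** Check which unit the laboratory data actually hold, then do one of the following in both 5.2.22 and Table 4:

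1. If the unit is umol/L, print 1710, 3420, 5700 and 11400 for triglycerides (1710 in Table 4) and 4000 to 6100 for glucose.
2. If the unit is umol/dL, keep the numbers and correct the label.
3. Convert the results held in that unit to mmol/L (divide by 1000 if umol/L, by 100 if umol/dL) and delete the umol/L limits.

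Leave the limits for the other units as they are, with one correction: in the top triglyceride class, change the 1000 g/L entry to 1000 mg/dL. Also confirm against the source SAP whether the mmol/L triglyceride row of Table 4 should include 1.71 in the normal range, as the other unit rows include their limit. It reads as strictly below 1.71, with high strictly above, which leaves 1.71 itself unassigned; the sign may have been lost when the PDF was converted to text.

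The cost is a few words in the SAP and one check of the units in the database. Data collection does not change.

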5.2.23 Subgroup

Five subgroups will be studied:

STATISTICAL ANALYSIS PLAN		
InFlectis BioScience	Sponsor:	InFlectis BioScience
	Protocol Number:	P288ALS
VERSION 1.0 NOV 12, 2024		

- Baseline NFL (neurofilament light chain): \leq median vs $>$ median defined according to the median of baseline NFL of the FAS.
- Country: France vs Italy
- Sex: Man vs Woman
- ALSFRS-R progression rate (point/month) (from symptoms onset to screening visit): \leq median vs $>$ median according to the median of ALSFRS-R progression rate of the FAS.
- Time from onset date of first ALS symptoms to screening: \leq median vs $>$ median according to the median of time from onset date of first ALS symptoms to screening of the FAS.

5.3 Conventions

All data listings, summaries, figures and statistical analyses will be generated using SAS version 9.4 or higher Erreur ! Source du renvoi introuvable.

Summaries will be presented by treatment group or overall. Treatment group labels will be displayed as follows:

IFB-088	Placebo
(N=XX)	(N=XX)

Listings will be sorted in the following order: treatment group, patient, visit and parameter unless otherwise stated. All data will be listed, and screen failures will be displayed after randomized and/or treated patients in applicable listings (e.g. patient disposition).

Continuous variables will be summarized by the number of non-missing observations, mean, median, standard deviation (SD), standard error (SE), first and third quartile, minimum and maximum.

Categorical variables will be summarized by presenting the frequency and percent. Percentages will be based on the number of subjects in the column header unless otherwise specified in the footnote. For each variable, all categories will be shown. Zero frequencies (but not the percent) within a category will be presented.

Means, medians, and percentiles will be displayed to one more decimal place than the data, dispersion statistics (e.g., SD) will have two more decimal places, and the minimum and maximum will be displayed to the same number of decimal places as reported in the raw data. Percentages will be displayed with one decimal place.

STATISTICAL ANALYSIS PLAN		
InFlectis BioScience	Sponsor:	InFlectis BioScience
	Protocol Number:	P288ALS
VERSION 1.0 NOV 12, 2024		

P-values will be quoted to 4 decimal places consistent with SAS PVALUEw.d format set to PVALUE6.4. P-values < 0.0001 will be presented as p<0.0001.

5.4 Patient Disposition

Subject disposition will be summarized as follows:

- The number of patients who failed screening and the reasons for failure will be tabulated for the Screened Set.
- The number of patients who were screened, randomized, treated, randomized or treated (i.e. enrolled) and who are in each analysis set will be summarized by treatment group and overall for the Screened set.
- The number of patients completing the study and those prematurely discontinuing the study as well as the reasons for discontinuation will be tabulated by treatment group and overall.
- The number of patients present at each scheduled visit will be summarized by treatment group.
- The reasons for exclusion from the PPS will be summarized by treatment group and overall.
- Study duration (days) will be summarized by treatment group and overall in RS.
- Treatment duration (days) will be summarized by treatment group and overall in RS.

Early termination (ET) assessments as well as V3 bis will only be listed and not included in by-visit summary displays.

All patients disposition data will also be listed.

5.5 Protocol Deviations

Protocol deviations will be summarized by classification (minor, major) and category (e.g. study procedure, etc.). A listing of protocol deviations will be provided within Appendix 16.2 of the CSR.

5.6 Baseline description

The baseline description will be performed on the Randomized Set.

Demographic characteristics parameters will be described at screening by treatment group and overall:

- Sex,
- Age (years),

STATISTICAL ANALYSIS PLAN		
InFlectis BioScience	Sponsor:	InFlectis BioScience
	Protocol Number:	P288ALS
VERSION 1.0 NOV 12, 2024		

- Race,
- BMI
- Smoking habits,
- Temperature

5.7 Amyotrophic lateral sclerosis history

The following history of amyotrophic lateral sclerosis will be presented on the Randomization Set by treatment group and overall:

- Time from onset date of first ALS symptoms to screening (months),
- Progression rate at screening
- Time from ALS diagnosis to screening (months),
- Weight at first ALS symptoms onset (kg),
- Weight variation between first ALS symptoms onset and screening (kg) (calculated in the eCRF),
- Type of ALS (Familial, Sporadic, Unknown).

5.8 Medical History

The following parameters will be described on the Randomization Set by treatment group and overall at screened visit:

- Medical history
- Planned procedures
- Active psychiatric illnesses (y/n)
- Suicidal risk (y/n)

5.9 Concomitant Medications

Medications will be coded using the WHO Drug Classifications (Global version B3, or later).

The number and percentage of patients with at least one concomitant medication will be described by Medication Class (ATC Level 4) and Medication Name overall in the Randomized Set. In case a same patient reported the same medication (i.e. same medication as defined according to WHO Drug classification) several times during the study, only one occurrence will be reported. This table will be sorted by decreasing percentage of Medication Class (ATC Level 4) and Medication Name within Medication Class (ATC Level 4) for the overall column.

5.10 Treatment Compliance

The compliance will be described at V4 by treatment group and overall on the Randomized Set.

STATISTICAL ANALYSIS PLAN		
InFlectis BioScience	Sponsor:	InFlectis BioScience
	Protocol Number:	P288ALS
VERSION 1.0 NOV 12, 2024		

5.11 Efficacy Analyses

5.11.1 General Considerations

The final version of the SAP will be finalized prior to the unblinding of data and database lock.

Analyses on Randomized Set and Full Analysis Set will be performed on randomized treatment.

Analyses on Per Protocol Set and Safety Set will be performed on actual treatment received.

5.11.1.1 Nominal alpha level of significance

As the trial is a safety trial and an estimation efficacy study and as it is not powered for efficacy endpoints, all tests performed on efficacy assessments were planned to be conducted at a 2-sided nominal alpha level of 0.20. 2- sided 95% confidence intervals will be provided.

5.11.1.2 Multiplicity

As it is an efficacy estimation trial, there will be no adjustment for multiplicity.

5.11.1.3 Missing data handling

Handling missing data is specified in the analysis of each endpoint.

Missing data will not be replaced for descriptive analyses.

5.11.2 Analysis of Change in ALSFRS-R

5.11.2.1 Expressions

This parameter will be expressed in terms of:

- Value at baseline and at each planned visit (baseline (V0), V3, and V4).
- Change from baseline to each post baseline visit.
- Change from V3 to V4.

For ALSFRS-R subscores and ALSFRS-R total score.

5.11.2.2 Change in ALSFRS-R total score from baseline to Month 6 (V4)

5.11.2.2.1 Primary analysis

The primary analysis of the Change in ALSFRS-R total score from baseline to Month 6 will be conducted on the FAS patients with a non-missing baseline ALSFRS-R total score as described in Table 1.

Missing data will be handled as described in Table 1 for estimand #1.

STATISTICAL ANALYSIS PLAN		
InFlectis BioScience	Sponsor:	InFlectis BioScience
	Protocol Number:	P288ALS
VERSION 1.0 NOV 12, 2024		

The change in ALSFRS-R score from baseline to Month 6 will be analyzed using an analysis of covariance (ANCOVA) model including treatment (IFB-088 vs placebo), and baseline ALSFRS-R score as continuous covariates. LS mean change with SE and 95% CI by treatment group and the difference in the LS means between 088 and placebo along with SE and 95%CI and p-value will be provided for estimand #1.

Residuals normality will be checked. Homogeneity of slopes across treatment groups will be investigated in an ANCOVA model including an additional term for treatment by baseline ALSFRS-R interaction.

